## 5.1 Study Procedures After 52 Weeks of study treatment

(For patients who are continuing treatment or re-starting treatment after progression of disease after 52 weeks, this table should not be used for patients who stay on therapy due to pseudoprogression)

Visit Number		1	2	3	4	5	6
Procedure/Study Day	Re-Evaluation before re-treatment	D1 **	D14 (±3D)	W4 (±3D)	W6 (±3D)	W8 *** (±3D)	
Durvalumab 750mg*		X	X	X	X	X	
CT chest, abdomen, pelvis; nuclear bone scan 	X					X	
Assessment of AEs/SAEs	X	X	X	X	X	X	
Concomitant medications	X	X	X	X	X	X	
Physical examination  , weight	X	X	X	X	X	X	
ECOG performance status	X	X	X	X	X	X	
Vital signs 	X	X	X	X	X	X	
Serum chemistry 	X	X		X		X	
lactate dehydrogenase, GGT, lipase, uric acid and amylase 	X	X				X	
Hematology 	X	X		X		X	
Coagulation parameters 	X	X				X	
Thyroid function tests 	X	X				X	

\* Treatment for this patient population will be Durvalumab monotherapy. On each treatment day, hematology, serum chemistry are to be resulted before treatment can begin.

\*\* The maximum time interval between re-evaluation study procedures and the first dose of study drug will be 14 days

\*\*\* Visits 2 through 6 will repeat for a total of up to 26 doses of durvalumab (52 weeks of therapy total), or until progressive disease (see 4.1.1) or unacceptable toxicity, with CTs and bone scans done every 8 weeks. Scans are to be completed every 8 weeks, regardless of drug holds or treatment delays.

 The same modality used at initial baseline should be used. Scans to be completed every 8 weeks, regardless of drug holds or treatment delays.

Note: Bone scans will be done only if the patient has bone disease. PET-CT is acceptable in place of bone scan, if a bone scan is contra-indicated for a

patient's disease. The same modality used at baseline should be used throughout. For patients with skin lesions, photographs may be taken on study-provided camera by study staff on a white background (wall of patient room) using a ruler measurement on a study supplied digital camera. Photographs should not include any identifying characteristics

 Serum Chemistry Panel will include calcium, chloride, magnesium, creatinine, sodium, potassium, blood urea nitrogen, bicarbonate, glucose, total bilirubin, aspartate aminotransferase (AST), alanine aminotransferase (ALT), alkaline phosphatase (ALP), albumin, total protein and creatinine clearance. If Total bilirubin is  $\geq 2 \times \text{ULN}$  (and no evidence of Gilbert's syndrome) then fractionate into direct and indirect bilirubin. Additional chemistry labs will include: lactate dehydrogenase, GGT, lipase, uric acid and amylase. During maintenance monotherapy, labs should be monitored every 8 weeks.

 Hematology will include basophils, eosinophils, lymphocytes, platelet count, monocytes, neutrophils, red blood cell count, total white cell count, hematocrit, mean corpuscular hemoglobin, mean corpuscular hemoglobin concentration, mean corpuscular volume, and hemoglobin.

 Coagulation parameters will include prothrombin time, partial thromboplastin time, and fibrinogen.

 Thyroid function tests will include thyroid stimulating hormone, free T3, and free T4.

 Systemic imaging (CTs, bone scan or PET-CT) may be performed up to 28 days prior to D1. Refer to footnote 1 for instructions regarding bone scan, PET-CT and skin lesions.

 Full physical examinations will include assessments of the head, eyes, ears, nose, and throat and the respiratory, cardiovascular, GI, urogenital, musculoskeletal, neurological, dermatological, hematologic/lymphatic, and endocrine systems. Height will be measured at screening only. Targeted physical examinations are to be utilized by the Investigator on the basis of clinical observations and symptomatology. Situations in which physical examination results should be reported as AEs are described in Section 10

 Vital signs (blood pressure [BP], pulse, temperature) will be evaluated according to the assessment schedules outlined in Section 4.2.1.

## 6.0 ENDPOINT ASSESSMENT

### 6.1 Definitions

#### 6.1.1 Measurable Lesions

Must be accurately measured in at least one dimension (greatest diameter) with a minimum size of 10mm by CT scan (cuts of 5mm or less), MRI, or physical exam (ideally using calipers). Bone only disease is allowed, however, must have an osteoblastic component that can be easily measured.

*Note: In case of skin lesions, patients will have standardized digital photography of their disease site for disease assessment. Photographs will be taken at the same time points as the CT scans (as indicated in the study procedures table in Section 5). Frontal and lateral photographs will be taken by study staff on a white background (wall or curtain in patient room) using a ruler measurement on a study supplied digital camera. Photographs should not include any identifying characteristics.*

#### 6.1.2 Non-measurable Lesions

Defined as all other lesions less than 10mm. Examples of non-measurable lesions include leptomeningeal disease, ascites, pleural/pericardial effusions, inflammatory breast disease, lymphangitic involvement of skin or lung.

#### 6.1.3 Response criteria

**Complete Response** - Disappearance of all lesions.

**Partial Response** - At least a 30% decrease in the sum of the diameters of target lesions, taking as reference the baseline sum diameters.

**Progressive Disease** - At least a 20% increase in the sum of diameters of target lesions, taking as reference the smallest sum on study (this includes the baseline sum if that is the smallest on study). In addition to the relative increase of 20%, the sum must also demonstrate an absolute increase of at least 5 mm. (Note: the appearance of one or more new lesions is also considered progression.)

**Stable Disease** - Neither sufficient shrinkage to qualify for PR nor sufficient increase to qualify for PD, taking as reference the smallest sum of diameters while on study.

#### 6.1.4 Immune-related RECIST

In addition to above, tumor response will be assessed by the irRECIST for investigational purposes, not assessment of primary objective (25). Tumor response by irRECIST is defined as an immune-related PR (irPR) or CR (irCR) over a period of at least 4 weeks. We will define immune-related clinical benefit rate as immune-related stable disease (irSD), irPR, or irCR.

### 6.2 Primary Endpoint

The primary endpoint is Overall Response Rate (ORR), defined as number (%) of patients with one visit response of partial response (PR) or a complete response (CR) in patients with metastatic HER2 negative breast cancer (TNBC in expansion cohort) treated with durvalumab in combination with tremelimumab using the Response Evaluation Criteria in Solid Tumors (RECIST) Version 1.1 (23). Patients who experience pseudoprogression and have subsequent response may count toward ORR. Evaluable patients must have had received 2 cycles of therapy and had 2 month scans.

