Pseudoprogression has been well-described in various studies in investigating checkpoint inhibitors, and refers to the inflammatory response that looks like progression of disease. This phenomenon is actually seen in the phase 1 study this proposal is based on (Figure 4 on abstract), but has also been observed in numerous other trials (PMID: 21785048). It is crucial for drug development of immunotherapy to capture pseudoprogression in a safe manner, therefore this proposal has been designed to anticipate pseudoprogression and allow for continued treatment provided that very specific criteria are met.

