**4.0 TREATMENT PLAN**

**4.1 Overview**

Non-randomized, open-label, pilot phase II clinical trial of durvalumab in combination with tremelimumab in patients with stage IV HER2 negative breast cancer, with an expansion cohort of TNBC.

Patients will be treated durvalumab 1500mg intravenously (IV) every 4 weeks for a total of 4 doses, and tremelimumab 75mg IV every 4 weeks for a total of 4 doses. After completion of the 4 doses of combination therapy (induction phase), durvalumab will be continued at a dose of 750mg every 2 weeks for up to 18 additional doses (maintenance phase), or until progressive disease (see 4.1.1) or unacceptable toxicity. The first 750mg dose of durvalumab will be 4 weeks after the last combination dose. Patients may continue on therapy after progression or after initial 52 week treatment period as specified in Sections 4.1.1 and 4.1.2. Patients will be followed for 3 years or until time of death. Overall response rate (ORR), clinical benefit rate, PFS, and OS will be determined. In addition, patient's next line of therapy will be monitored for response rates and duration of clinical benefit to next line therapy.

Patients will undergo a fresh tissue biopsy prior to study enrollment and two months after treatment, unless deemed to be clinically inappropriate per PI or co-investigator, to evaluate pharmacodynamic changes in immune-related biomarkers. Correlatives will be assessed.

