**4.1.1 Continuation of Investigational Therapy after Radiographic Progression (Pseudoprogression)**

Treatment may be continued in the setting of pseudoprogression (radiographic increase or new lesions felt to be due to inflammation/immune response) as long as all of the following criteria are met:

- Absence of clinical symptoms or signs indicating clinically significant PD.
- No significant decline in Eastern Cooperative Oncology Group (ECOG) performance status (PS >2 or as deemed by treating investigator).
- Absence of rapid PD or threat to vital organs/critical anatomical sites (e.g., spinal cord compression) requiring urgent alternative medical intervention
- Patients are made aware of the potential benefits and risks of continuing study therapy in the setting of Pseudo-Progression. Patients continuing therapy in the setting of suspected pseudoprogression should continue with treatment according to whether they in the induction phase (durvalumab 1500mg intravenously (IV) every 4 weeks for a total of 4 doses, and tremelimumab 75mg IV every 4 weeks for a total of 4 doses) or maintenance phase (durvalumab 750mg every 2 weeks). For example, a patient with suspected pseudoprogression after cycle 2 of durvalumab and tremelimumab would continue onto cycle 3 of durvalumab and tremelimumab rather than durvalumab single agent portion of the regimen (maintenance phase).

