#### 4.6 Duration of Therapy

Patients may continue for 12 months of treatment or until any of the following occur:

- Disease progression
- Development of an inter-current illness that prevents further administration of treatment
- Unacceptable adverse event(s)
- Patient decides to withdraw from either study treatment or the as a whole study
- The treating investigator determines that the patient should be taken off treatment for any reason (i.e. changes in condition, inability to comply with study treatment or procedures)

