#### **10.3**

#### **Data Analyses Plans**

The primary analysis will be on the intent-to-treat (ITT) population, including all evaluable patients. Best ORR defined as will be defined as number (%) of patients with at least one visit response of complete or partial response by the Response Evaluation Criteria in Solid Tumors (RECIST 1.1). Best objective response prior to disease progression will be used. The overall response rate will be estimated by the proportion of overall response, and its 80% confidence interval (CI) and 95% CI will be estimated using the exact binomial distribution.

Additionally, we will evaluate clinical benefit rate, defined as stable disease for  $\geq 12$  weeks complete or partial response using RECIST 1.1 guidelines in a similar manner. We will also perform similar analyses using Immune Related RECIST (irRECIST).

PFS is defined as the time from date of treatment initiation until date of documented disease progression or death (by any cause in the absence of progression). OS is defined as the time from the date of start of treatment until death due to any cause. For patients alive at the time of data cut-off, PFS and OS will be censored as of the last tumor assessment date or known to be alive, respectively. The PFS and OS will be estimated using the Kaplan-Meier method. The number, frequency, and severity of adverse events (as defined by the NCI Common Terminology Criteria for Adverse Events or CTCAE version 4.03) will be recorded.

Baseline percent PDL1 expression, TILs (sTILs, iTILs, and their ratio), and changes in T cell subpopulations will be used as a continuous variable to predict clinical benefit or overall response rates using appropriate statistical summaries. Cox proportional hazards regression will be used to compare how these biomarkers are associated with PFS and OS as well.

Changes from baseline in these biomarkers will also be analyzed to assess for pharmacodynamic effects of treatment. Continuous variables will be analyzed using either paired t-tests, signed rank tests or repeated measures analysis of variance.

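### The primary response rate has no fixed rule for a response after pseudoprogression: Section 6.2 makes counting it optional, and Section 10.3 stops at disease progression without saying whether pseudoprogression is included

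*Combined protocol and SAP*

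**What the plan says.** Section 6.2 scores the primary endpoint by RECIST 1.1, accepts a response seen at a single visit, and adds: "Patients who experience pseudoprogression and have subsequent response may count toward ORR". It names no criterion for counting, and it does not define the later response.

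Section 10.3 gives the analysis rule: "Best objective response prior to disease progression will be used".

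The surrounding text is as follows.

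- Section 6.1.3 treats any new lesion as progression, with no exception for pseudoprogression.
- Section 6.1.4 keeps irRECIST out of the primary objective and requires an irRECIST response to last at least 4 weeks.
- Section 4.1.1 describes pseudoprogression as "radiographic increase or new lesions felt to be due to inflammation/immune response" and uses the idea to decide on continued treatment, not to classify response.
- Sections 2.1 and 10.1 restate the primary endpoint without mentioning pseudoprogression.
- Section 1.7.3 reports one triple-negative (TNBC) patient whose lymph nodes enlarged. The patient was scored as progressive disease, after which the nodes were stable and the target lesions showed a partial response.

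**The concern.** A primary endpoint needs a rule that gives one answer for each patient, whoever applies it and whatever the results look like. Here the analyst can include or leave out a late responder after seeing the response, and both choices comply with Section 6.2. The cohorts are small, so one patient is a visible share of the result, and both decision rules are simple counts (6 of 27 and 8 of 20).

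A second gap sits inside the first. Section 6.2 does not say whether a partial response in target lesions counts as the later response when the lesions that triggered progression are still enlarged. That is the only case the documents describe.

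**Working it through.** **1. Does Section 10.3 exclude these responses?** The passages point in both directions.

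| Suggests pseudoprogression is not progression | Suggests that it is |
|---|---|
| Section 1.7.2: it "refers to the inflammatory response that looks like progression of disease" | Section 4.1 describes treatment under 4.1.1 as coming after progression: "Patients may continue on therapy after progression or after initial 52 week treatment period as specified in Sections 4.1.1 and 4.1.2" |
| Section 4.6: "Patients may continue for 12 months of treatment or until any of the following occur", with disease progression listed first, while 4.1.1 lets treatment continue through pseudoprogression | Section 6.1.3 has no exception, and the Section 1.7.3 table scores the one such patient as progressive disease |

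On the left-hand reading, Section 6.2 permits inclusion but does not require it. On the right-hand reading, Section 6.2 permits what Section 10.3 excludes. Neither reading gives a fixed rule.

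**2. First 18 evaluable patients.** The inputs are from Section 1.7.3: 3 partial responses in 18 patients, all 3 among the 7 with TNBC, and one further TNBC patient with pseudoprogression.

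- The plan's figures reproduce: 3/18 = 16.7% and 3/7 = 42.9%.
- With that patient counted: (3+1)/18 = 4/18 = 22.2% and 4/7 = 57.1%. The shifts are 1/18 = 5.6 points overall and 1/7 = 14.3 points in TNBC.

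Section 10.3 says of the rate that "its 80% confidence interval (CI) and 95% CI will be estimated using the exact binomial distribution". The exact limits for x of n are the α/2 quantile of Beta(x, n−x+1) and the 1−α/2 quantile of Beta(x+1, n−x).

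| Count | 95% CI | 80% CI |
|---|---|---|
| 3/18 | 3.6 to 41.4% | 6.3 to 33.4% |
| 4/18 | 6.4 to 47.6% | 10.1 to 39.6% |

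**3. Expansion cohort.** Section 10.2 gives a Beta(0.3, 0.7) prior and a threshold of 8 of 20. The posterior for x responses is Beta(0.3+x, 0.7+20−x).

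- x = 8: Beta(8.3, 12.7), P(ORR > 30%) = 0.81. This reproduces the plan's 0.81.
- x = 7: Beta(7.3, 13.7), P(ORR > 30%) = 0.66.

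**4. Two-stage design in Section 10.2.** The rule is at least 2 of 11, then at least 6 of 27. Summing P(X₁ = x)·P(X₂ ≥ 6−x) over x from 2 to 11, with X₁ binomial on 11 and X₂ binomial on 16, gives:

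- type I error 0.0395 at 10% (stated 4%)
- power 0.806 at 30% (stated 80%)
- early stopping 0.697 at 10% (stated 70%)

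One reclassified patient at the boundary moves 5/27 (18.5%) to 6/27 (22.2%). The chance of continuing and finishing on exactly 5/27 is 5.55% at a true rate of 10%, 13.3% at 20% and 5.35% at 30%. The ambiguity can therefore decide the result, but only in a minority of outcomes, and only if such a patient exists.

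**The case against.** The strongest defence is that there is no contradiction. Section 6.2 is the specific rule, Section 10.3 the general one, and disease progression in 10.3 means true progression. Sections 1.7.2 and 4.6, read with 4.1.1, support this. That much stands: a reader might infer a flat contradiction, and the documents show only an ambiguity. The defence does not remove the optional wording, though.

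Four stronger readings are tempting, and the documents do not support them.

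- *Type I error more than doubles.* Crediting one extra response at the final look takes 0.0395 to 0.0950, but only if a creditable patient is always available and the 10% null refers to strict RECIST 1.1. The documents give no such availability. If late responses belong to the endpoint, the null applies to that endpoint and nothing is inflated.
- *The patient moves the result past the null.* The lower 80% limit goes from 6.3% to 10.06%, against a null stated as approximately 10%. No section makes a confidence limit a decision rule, and both 95% intervals include 10%.
- *Section 1.7.3 already scores the patient both ways.* Its text and table report the same ORR (42.9%) and clinical benefit rate (71.4%). The remark about 6 of 7 patients concerns benefit in a loose sense and is neither endpoint.
- *The patient decides whether the trial continues.* Section 3.0 asks for 4 of 18, but Section 10.2 asks for 2 of 11. Which rule governs is a separate question.

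The irRECIST analyses planned in Section 10.3 cover part of the gap. Because irRECIST needs a response over at least 4 weeks, they do not show what the one-visit primary endpoint would be under the other rule.

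**Conclusion.** The point holds: the plan leaves inclusion in the primary ORR to discretion, whichever way Section 10.3 is read. In the first 18 patients the size is one patient: 16.7% or 22.2% overall, and 42.9% or 57.1% in TNBC. The higher figures rest on two assumptions that the documents do not settle: that the Section 6.2 allowance is used, and that a target-lesion partial response with stable enlarged nodes is a response. The figures for 7/20 against 8/20 and 5/27 against 6/27 show what one patient does at the threshold. They are not forecasts. The documents do not show that 27 evaluable patients were reached, and Appendix E records closure for low accrual.

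On timing, Appendix E places both the pseudoprogression wording and the Section 1.7.3 results in Amendment 8, so for the first 18 patients the wording was not set blind to the data. A reader might extend that to the whole trial. The documents do not support this, because the same amendment created the expansion cohort and the wording therefore preceded that cohort's data. Nothing here shows intent. The matter should be fixed before the ORR is reported.

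**What to change.** Replace the optional wording in Section 6.2 with one mandatory rule and state it identically in Section 10.3. Either choice is workable.

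- *Strict:* best RECIST 1.1 response before the first RECIST 1.1 progression. The Section 1.7.3 table already scores its patient this way.
- *Inclusive:* responses after pseudoprogression will count, with a definition of the later response that covers persisting new or enlarged lesions. This endpoint should not be labelled plain RECIST 1.1.

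Report the other version as a labelled sensitivity analysis. State that for the first 18 patients the rule was set after their data were seen. The same label applies to the expansion cohort only if the new rule is fixed after that cohort's data are seen.

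The cost is one sentence in each section and one table line. Under the strict rule the primary ORR may be lower by about one patient, and the late responses the protocol wants to capture would appear only in the sensitivity and irRECIST analyses. The change concerns scoring only and takes no position on continuing treatment.

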### 6.3 Secondary Endpoints

Secondary endpoints include PFS and OS, where PFS is defined as the time from date of treatment initiation until date of documented disease progression or death (by any cause

in the absence of progression), and OS is defined as the time from date of treatment initiation until death due to any cause.

Clinical benefit rate will be assessed and defined as SD (for  $\geq$  12 weeks) + PR + CR. Any patient who has completed two months of study therapy is evaluable for this end point

The number, frequency, and severity of adverse events (as defined by the NCI Common Terminology Criteria for Adverse Events or CTCAE version 4.03) will be recorded. Any patient treated with minimum 1 dose of either study drug will be evaluable for toxicity.

